Efficacy and safety data from the Phase 1/2 study, Study 200, and the Phase 3 study, Study 3000, are presented below according to phase of disease and line of therapy, as of 28 March 2011 for efficacy and 15 February 2012 for safety (Study 200) and as of 26 September 2011 (Study 3000). Pooled safety data from Study 200, Study 3000, and the Phase 1/2 Japanese study, Study 2203, are presented below as of 15 November 2010. The most current safety data are contained in the Investigator's Brochure.

Second-Line CP CML

A total of 288 CP CML patients were enrolled and treated in the second-line setting in Study 200. The primary population for the efficacy response analyses was the evaluable population for imatinib-resistant patients, which included all treated patients with an adequate baseline assessment for the respective endpoint. The major cytogenetic response (MCyR) rate at Week 24 in the primary cohort (imatinib-resistant second-line CP CML) for the evaluable population (n=186) was 35.5%, with 24.2% attaining complete cytogenetic response (CCyR). Cumulative MCyR (defined as any on-treatment MCyR response during that period) was achieved in 55.4% of patients, with 43.0% attaining a CCyR. Cumulative MCyR and CCyR were newly achieved or maintained from baseline in 58% and 46% of patients, respectively. For patients with imatinib-intolerant CP CML, the MCyR rate at Week 24 in the evaluable population (n=80) was 30.0%, with a 25% CCyR rate at Week 24. Cumulative MCyR was achieved in 48.8% of patients, with 42.5% attaining a CCyR. Cumulative MCyR and CCyR were newly achieved or maintained from baseline in 61% and 54% of patients, respectively.

In the evaluable population of second-line CP CML (n=287), 85.0% achieved cumulative CHR, a secondary endpoint defined as a confirmed CHR or maintenance of baseline CHR during treatment with bosutinib. Of the 141 patients who did not have a CHR at baseline, 77.3% achieved a confirmed CHR. The Kaplan-Meier (K-M) estimates of PFS for the CP CML second-line all-treated population (n=288) were 91.3% and 80.6% at Year 1 and Year 2, respectively; the K-M median PFS has not been reached. The K-M estimates of overall survival (OS) were 96.8% and 90.6% at Years 1 and 2, respectively; the K-M median OS has yet to be reached.

Third-Line CP CML

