5.4. Other Analysis Sets

The evaluable analysis set are those treated patients with a valid baseline efficacy assessment for the respective endpoint (ie, [1] at least 20 metaphases from the baseline bone marrow cytogenetic assessment or a CCyR with at least 200 cells analyzed from the fluorescence in situ hybridization [FISH] baseline assessment or MMR from the baseline molecular assessment for cytogenetic endpoints or [2] a valid baseline hematologic assessment for hematologic endpoints as defined in [Appendix 1](#) or [3] a valid baseline molecular assessment from the central laboratory for molecular endpoints).

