Cumulative response is any response on-treatment. Landmark “at” responses need to occur within a 2 week window of the landmark for those before Week 39 and within a 4 week window for Week 39 and after (eg, Month 3 is \geq Week 11 to \leq Week 15, Month 18 is \geq Week 74 to \leq Week 82, etc.). Molecular responses are defined in [Appendix 2](#). Response is unconfirmed for cytogenetic and molecular and confirmed for hematologic with 2 consecutive responses at least 28 days apart. The date of hematologic confirmed response is the date of the first response. To be considered a responder, the patient must have maintenance of baseline response while on-treatment or an improvement from baseline. The hierarchy to assess for best response from best to worst is \geq 4.5-log reduction of BCR-ABL transcripts from standardized baseline on the international scale (MR^{4.5}), MR⁴ (\geq 4-log reduction), MMR (\geq 3-log reduction, same as MR³), CCyR, PCyR, CHR, and OHR.

Duration of response (DOR) for CCyR and MMR, is defined as the time from first response to confirmed loss, progression of disease as assessed by the investigator, or on-treatment death due to any cause ([date of loss – date of first response + 1]/30.4). For CCyR, confirmed loss is defined as 2 consecutive assessments with >0 Ph+ metaphases at least 28 days apart. For MMR, confirmed loss is defined as 2 consecutive assessments at least 28 days apart with a <3 -log ($>0.1\%$) reduction in transcripts from standardized baseline one of which corresponds to a \leq 2-log reduction ($\geq 1\%$). The date of confirmed loss is the earlier of first loss, progression, or death date. Patients without confirmed loss, progression, or death are censored at the last valid assessment where response could be assessed.

Exploratory

- *PFS.*
- *OS.*
- *Presence of BCR-ABL mutations.*
- *For Ph- CML patients, cumulative best response (OHR and MMR) anytime on treatment.*
- *Patient reported outcome (PRO) endpoints as measured by Functional Assessment of Cancer Therapy-Leukemia (FACT-Leu).*
- *To collect banked biospecimens for exploratory research, unless prohibited by local regulations or ethics committee decision. Collection of banked biospecimens unless prohibited by local regulations or ethics committee decision. Additional information on collection and potential use is provided in the Banked Biospecimens section.*

- Time to MMR, MR⁴, MR^{4.5}, CCyR, and MCyR.
- Duration of MR⁴ and MCyR.

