- Time to confirmed transformation on-treatment.

The local cytogenetic assessments will be used for the exploratory endpoint analyses for all patients. The local hematologic assessments will be used for the exploratory endpoint analyses for all patients. *Molecular assessments will be performed at a central laboratory. Endpoint analysis for molecular response will be carried out by independent central analysis.*

Time to response is the time from first dose to first response, unconfirmed for molecular and cytogenetic ([date of first response – first dose date +1]/30.4). Patients without events are censored at the last molecular or cytogenetic assessment where response could be assessed for the respective endpoint.

DOR for MCyR follows the same rules as the secondary endpoint of DOR for CCyR. DOR for MR follows the same rules as the secondary endpoint of DOR for MMR except confirmed loss is defined as 2 consecutive assessments at least 28 days apart with a <4-log (>0.01%) reduction in transcripts from standardized baseline one of which corresponds to a \leq 3-log reduction (\geq 0.1%).

PFS is defined as the time from first dose to objective progression or relapse as assessed by the investigator and noted as the reason for permanent treatment discontinuation on the case report form (CRF) or on-treatment death due to any cause ([date of progression – first dose date +1]/30.4). Patients without events are censored at the last cytogenetic, hematologic, or laboratory assessment where progression could be assessed. Progression is defined as:

- *For CP, at least one of the following criteria:*
 - *Development of AP or BP CML;*
 - *Loss of CHR (in absence of cytogenetic response) confirmed by 2 complete blood counts (CBC) at least 2 weeks apart; Loss of CHR is defined as:*
 - *WBC count that rises to $>20.0 \times 10^9/L$;*
 - *Platelet count that rises to $\geq 600 \times 10^9/L$;*
 - *Appearance of extramedullary disease not present at baseline including hepatosplenomegaly by palpation or other extramedullary involvement proven by biopsy;*
 - *Appearance of $\geq 5\%$ myelocytes + metamyelocytes in the peripheral blood or appearance of blasts or promyelocytes in the peripheral blood;*
 - *Loss of MCyR (loss of CCyR or loss of PCyR);*

- *Increasing white blood count (WBC) in a patient without CHR, defined as doubling of WBC, to $>20 \times 10^9/L$ on 2 occasions at least 2 weeks apart (after the first 4 weeks of treatment).*

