8.2.2. Analysis of Secondary Efficacy Endpoints

The response rate and DOR analyses are based on the evaluable analysis set for Ph+ CML patients only. The efficacy analysis is the percentage of responders cumulative anytime on-treatment or at a specific landmark, for:

- Cumulative MCyR separately for CP, AP, and BP;
- Cumulative confirmed OHR separately for AP2L, AP3L, AP4L, BP2L, BP3L, BP4L;
- Best response separately for CP, AP, and BP;
- Landmark MCyR at 3, 6, 12, 18, and 24 months separately for CP, AP, and BP;
- Landmark confirmed OHR at 3, 6, 9, 12, 18, and 24 months separately for AP and BP;
- Cumulative confirmed CHR separately for CP, AP, and BP;
- Cumulative MMR separately for CP, AP, and BP;
- Duration of CCyR separately for CP, AP, and BP;
- Duration of MMR separately for CP, AP, and BP.

Any patient not demonstrating a response on-treatment for cumulative and at the specific visit for landmark is deemed a non-responder for the respective analysis. For landmark analyses, if the patient is missing the landmark assessment however the patient is responding at the scheduled before and after visit (eg, missing Month 6/Week 26 but responding at Week 13 and Week 39, missing Month 18/Week 78 but responding at Week 52 and

Week 104, etc.), then the patient will be deemed a responder for that landmark. For cumulative MMR (including MR⁴ and MR^{4.5}) and MCyR (including CCyR), supportive analyses will be provided excluding patients with baseline response and also for patients who responded before and after initial dose reduction to 400 mg, 300 mg, and 200 mg due to an AE

The duration of cytogenetic and molecular response analyses are based on the evaluable analysis set for the subset of patients who respond for the respective endpoint. The K-M method, as described in [Section 8.1](#), will be used for estimation of the distributions of duration provided most responding patients remain on treatment until progression or loss of response. The percentages of CCyR and MMR for the respective endpoint, along with percent of censored patients still on-treatment and percent of reasons for failure will be summarized.

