8.2.3. Analysis of Exploratory Efficacy Endpoints

The time to molecular and cytogenetic response analyses are based on the evaluable analysis set. Cumulative incidence of response adjusting for the competing risk of treatment discontinuation due to any reason without response, as described in [Section 8.1](#), will be used. The percentage of responders without treatment discontinuation and the percentage of treatment discontinuation without response will be summarized.

The duration of cytogenetic and molecular response exploratory analyses follow the same rules as the secondary DOR analyses except the percentages of MCyR, CCyR, and PCyR and MR⁴ will be summarized.

The time to transformation analysis is based on the full analysis set. Cumulative incidence of transformation adjusting for the competing risk of treatment discontinuation due to any reason without transformation, as described in [Section 8.1](#), will be used. The percentage of transformation without treatment discontinuation and the percentage of treatment discontinuation without transformation will be summarized. The specific disease stage transformation (accelerated or blast phases) will also be listed.

The PFS analysis is based on the full analysis set. The K-M method, with or without insufficient clinical response as assessed by the investigator as an event or cumulative incidence of on-treatment progression or death adjusting for the competing risk of treatment discontinuation without the event, as described in [Section 8.1](#), will be used.

The OS analysis is based on the full analysis set. The K-M method, as described in [Section 8.1](#), will be used. The number of deaths and causes of death will be summarized. Time on study from date of first dose to date of last contact and reasons for discontinuing participation will also be summarized.

The percentage of patients with baseline and emergent mutations, along with the specific types of mutations, will be summarized. The percentage of patients with cumulative MCyR, CHR, MMR, and OHR (AP and BP patients only) by baseline mutation status will be provided. The distributions of PFS and OS will also be displayed for patients with a baseline mutation versus those assessed but without a baseline mutation.

The percentage of Ph- CML patients in each best response category will be summarized.

Missing values and incomplete data will be handled as described in [Section 7](#) of this analysis plan.

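### Time to MMR, MR4, MR4.5, CCyR and MCyR is analysed in the whole evaluable set, so a response carried in from the previous TKI and still present at the first on-treatment assessment counts as an onset event

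*SAP*

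**What the plan says.** The endpoints are listed in SAP 6.1 under Exploratory: "Time to MMR, MR⁴, MR^{4.5}, CCyR, and MCyR". Four parts of the SAP define the analysis.

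- **Population.** SAP 8.2.3: "The time to molecular and cytogenetic response analyses are based on the evaluable analysis set". SAP 5.4 defines that set: "The evaluable analysis set are those treated patients with a valid baseline efficacy assessment for the respective endpoint". For cytogenetic endpoints, a patient can qualify through a baseline CCyR by FISH on at least 200 cells, or through "MMR from the baseline molecular assessment for cytogenetic endpoints". Being in response at entry is thus one of the ways to become evaluable.
- **Event.** SAP 6.1: "Time to response is the time from first dose to first response, unconfirmed for molecular and cytogenetic". No improvement on baseline is required in that definition.
- **Imputation.** SAP 7 allows CCyR to be imputed on a date when MMR is shown, if molecular testing replaced cytogenetics.
- **Estimator.** SAP 8.2.3 uses cumulative incidence, with treatment discontinuation without response as the competing risk. SAP 8.1.4 tabulates yearly rates through year 4 for this method.

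The plan does deal with baseline responders for the cumulative MMR (with MR4 and MR4.5) and MCyR (with CCyR) percentages. SAP 8.2.2 says "supportive analyses will be provided excluding patients with baseline response". That sentence is confined to cumulative rates and is not repeated in 8.2.3.

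**The concern.** A time-to-response curve should show how soon and how often bosutinib produces a response in patients who could still attain it. A patient already in MMR on the previous TKI is not at risk of attaining MMR. If the patient is still in MMR at the first on-treatment sample, the recorded time reflects the visit schedule and not an onset on bosutinib. Through imputation, the same sample can also supply the CCyR and MCyR events.

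Entry in response is expected in this trial. Protocol 9.2.1 has a separate responder rule for patients who arrive in CCyR, and Protocol 4.1 waives the screening marrow for patients in MMR. The primary endpoint guards against easy credit: SAP 6.1 requires at least 52 weeks of maintained cytogenetic response or an improvement, and Protocol 9.2.1 counts MMR only if it is deeper than at baseline. The time-to-response definition has no equivalent safeguard. At stake is the reading of the early curve and the yearly rates: new responses and carried-in responses are mixed in unknown proportion.

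**Working it through.** **Plan's own figure.** The documents give no figure for time to response. The only precision figure is in Protocol 9.1, a standard deviation of at most 0.075 with 45 patients. It reproduces: √(0.5 × 0.5 / 45) = 0.0745. It matters here only for the cost of a smaller set (see the fix).

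**Step 1: does a carried-in response become an event?** The patient is in the analysis (SAP 5.4, 8.2.3). The first scheduled on-treatment cytogenetic and molecular assessment is Week 13 (Protocol Table 1). If the secondary-endpoint responder rule in SAP 6.1 carries over, a maintained baseline response counts. If it does not, the bare definition applies and any first response counts. Either way the event is dated at about Week 13, provided the response is still present. The SAP does not say this in one sentence; it follows from reading the sections together.

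**Step 2: effect on the curve.** Let b be the share in response at entry, m the share of those still responding at the first assessment, and F_new(t) the cumulative incidence in all other patients. From Week 13 on, ignoring carried-in responses that are lost and later regained:

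- F_all(t) = b·m + (1 − b)·F_new(t)
- inflation = F_all(t) − F_new(t) = b·(m − F_new(t))

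The inflation is positive whenever m exceeds F_new(t), and shrinks as F_new rises.

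**Step 3: an anchor for b.** The documents do not give this trial's baseline response distribution. Protocol 1.2.2 reports earlier second-line chronic-phase results both as responses achieved and as responses newly achieved or maintained. For the imatinib-intolerant group the latter reads: "Cumulative MCyR and CCyR were newly achieved or maintained from baseline in 61% and 54% of patients, respectively".

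| Earlier-study group | Response | Achieved | New or maintained | Difference (points of patients) |
|---|---|---|---|---|
| Imatinib-resistant | MCyR | 55.4% | 58% | 2.6 |
| Imatinib-resistant | CCyR | 43.0% | 46% | 3.0 |
| Imatinib-intolerant | MCyR | 48.8% | 61% | 12.2 |
| Imatinib-intolerant | CCyR | 42.5% | 54% | 11.5 |

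This takes each difference as the share of all patients with a carried-in response. The MCyR range is 2.6% to 12.2%.

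**Step 4: illustration.** Assumed: new responses of 10, 12, 8, 6, 8 and 6% at Weeks 13, 26, 39, 52, 78 and 104 in patients not in response at entry. F_new is then 10% at Week 13, 36% at Week 52 and 50% at Week 104. With m = 1:

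| | Week 13 | Week 52 | Week 104 |
|---|---|---|---|
| F_new | 10% | 36% | 50% |
| b = 2.6% | 0.026 + 0.974 × 0.10 = 12.3% | 0.026 + 0.974 × 0.36 = 37.7% | 0.026 + 0.974 × 0.50 = 51.3% |
| b = 12.2% | 0.122 + 0.878 × 0.10 = 21.0% | 0.122 + 0.878 × 0.36 = 43.8% | 0.122 + 0.878 × 0.50 = 56.1% |

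The inflation is 2.3 to 11.0 points at Week 13, 1.7 to 7.8 at Week 52 and 1.3 to 6.1 at Week 104.

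**Step 5: sensitivity to m.** The differences in Step 3 count maintained responses, so they are closer to b·m than to b. If b·m = 12.2% and m = 0.8, then b = 0.122 / 0.8 = 15.25%. The upper row becomes 0.122 + 0.8475 × F_new = 20.7%, 42.7% and 54.6%. The picture barely changes.

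**The case against.** The strongest defence is that the plan counts maintained response as response on purpose. SAP 6.1 says so for the secondary endpoints, and using one evaluable set keeps the curves consistent with the cumulative rates. That is fair for a percentage. It does not rescue a time, because a maintained response has no onset on bosutinib.

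Several limits do stand. The endpoints are exploratory, and SAP 4.2 has no decision rules. SAP 8.2.2 already shows how often new responses occur for the same five response levels, so only the timing and the yearly time-to-response rates are uncovered. SAP 6.4 permits further supportive analyses, but permission is not a plan. SAP 8.1.4 tabulates yearly rates, so the largest distortion, at Week 13, appears only in the shape of the early curve.

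Three stronger readings are tempting and not supported:

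- **That 20% or more of patients enter in response.** The 12.2 points are 20% of the 61% who responded (12.2 / 61), but only 12.2% of patients. The imatinib-resistant group gives 2.6 points. Nothing in the documents supports 20% or 40% of patients.
- **That every baseline responder is booked at Week 13 for every endpoint.** It applies only to those still in response. For MCyR, the primary-endpoint text of SAP 6.1 requires baseline-PCyR patients to attain CCyR; whether that rule applies to time to MCyR is not stated.
- **That cohorts with more intolerant patients will look faster only for this reason.** Cohorts are defined by phase and line (SAP 2.1), and no cohort comparison is planned. The documents support only that the distortion depends on the baseline mix.

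**Conclusion.** The concern holds in direction and is modest in size. Followed as written, SAP 8.2.3 counts carried-in responses that persist to the first on-treatment assessment as onset events, which makes the curves higher than the incidence of new response, most of all at the start. On the protocol's earlier-study MCyR figures the excess is about 2 to 11 points at Week 13, 2 to 8 at one year and 1 to 6 at two years.

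These figures rest on assumptions: the attainment rates in other patients, nearly all carried-in responses persisting to the first assessment, and a second-line chronic-phase population standing in for this trial. The true size depends on a baseline distribution that the documents do not give, and it may differ for the molecular endpoints. A reader should not infer that the primary analysis is affected: its own maintenance and improvement rules apply there. The change is worth making because it is cheap and the timing is what these endpoints exist to describe.

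**What to change.** In SAP 8.2.3, extend the SAP 8.2.2 exclusion of baseline responders to time to response:

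- Present each curve and its yearly rates in evaluable patients who do not have that response level or a better one at baseline. For time to MMR, that means not in MMR or deeper; for time to CCyR, not in CCyR or MMR.
- Report the number excluded from each curve, by cohort.
- State whether the rule that baseline-PCyR patients must attain CCyR applies to time to MCyR.
- The full evaluable-set curve may be kept alongside, labelled as including responses present at entry.

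No new data are needed, and the subset flag is already required for SAP 8.2.2. The cost is fewer patients per curve, notably in the 4th-line cohort, and less favourable onset figures. As a guide, if 12.2% of 45 patients were excluded, 45 × 0.878 = 39.5 would remain, and the maximum standard deviation of a response proportion would rise from 0.075 to √(0.25 / 39.5) = 0.080. The 45 span all three phases, so an individual curve would rest on fewer.

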8.2.4. Analysis of Safety Endpoints

The full analysis set will be used for all safety analyses unless specifically stated otherwise. The safety endpoints will be analyzed according to the cohorts or a combination of these cohorts as specified in [Section 2](#).

8.2.4.1. Baseline Characteristics

Listings of demography and baseline characteristics data will be provided. The baseline variables listed below will be summarized using descriptive statistics.

- Age in years;
- Race;
- Sex;
- Weight (kg);
- Height (cm);
- ECOG performance status;
- Cancer history (prior cancer history including CML, initial and current CML disease stage, duration since CML diagnosis);
- Prior cancer therapies (number of prior regimens for interferon, imatinib, dasatinib, and nilotinib), duration of prior therapy, and reasons for resistance/intolerance status of prior TKIs;
- Medical history by MedDRA System Organ Class (SOC) and PT.

8.2.4.2. Treatment and Compliance

Descriptive statistics for continuous exposure variable treatment duration and cumulative dose received and the received dose over time (% receiving 600, 500, 400, 300, 200, or 0 mg at specific time points) will be calculated.

The number and percentage of patients with at least one dose reduction due to AE, dose delay due to AE, and escalation to 600mg will be summarized. The number and percentage of patients who experienced more than 1 event will also be summarized.

The number and percentage for reasons for treatment discontinuation will be summarized and listed. A listing of COVID-19 related treatment discontinuations will be provided.

8.2.4.3. Laboratory Evaluations, Vital Signs, and Cardiac Evaluations

The incidence of clinical laboratory, QTcF/QTcB, and LVEF abnormalities by maximum toxicity grade will be presented at baseline, during the treatment period, and post treatment period. Shifts from baseline to maximum on-treatment grade for QTcF/QTcB and LVEF will also be presented.

Laboratory values and vital signs will be provided in the data listings.

